15.0 RISKS TO PARTICIPANTS

See "Risks & Safety" in PROCEDURES above

16.0 POTENTIAL BENEFITS TO PARTICIPANTS

Individual participants may experience an improvement in hot flashes as a result of this research, with secondary improvements in quality of life, mood and sleep.

17.0 STATISTICS, DATA MANAGEMENT AND CONFIDENTIALITY

Power Analysis

We derived our sample size estimates for the analysis of the primary endpoint for this study, i.e., change in weekly frequency of severe hot flashes at 6 months post-intervention vs. baseline (pre-intervention), based on data in the literature from a randomized controlled trial comparing different treatments for HF in men with prostate cancer on ADT. The pre-treatment baseline weekly frequency of severe hot flashes was assumed to be 46.0 ± 43 (mean \pm SD)³⁵.

Because there are no published data on the variability of within-person differences between the 6-month and baseline measures for severe hot flashes, we estimated the variance for this 6-month change variable using the equation for the variance of the difference between two possibly correlated measurements, as provided in the textbook by Rosner, 7th edition, pg. 305. This equation depends on the baseline standard deviation (SD1), the standard deviation of the 6-month assessment (SD2), and the within-person correlation (ρ) between the baseline and 6 month follow-up variables. We allowed the original baseline and 6-month SDs to differ at the two assessment times but varied the within-person correlation between pre- and 6-month post-treatment measurements (range: $\rho = 0.5$ to $\rho = 0.8$, in increments of 0.1).

The results below assumed a value of 21 for SD2 and assume the properties of the exponential distribution are approximately valid for the severe hot flashes measure (i.e., we assumed that the underlying mean and standard deviation are approximately equal).

Using a paired one-sample t-test comparing changes between 6-month assessment and baseline, a sample size of 14 participants will provide 80% power with a two-sided $\alpha = 0.05$ to detect a reduction of 52% in mean frequency of severe hot flashes ($\Delta = 23.9$) if $\rho = 0.8$ (e.g., from a mean of 46.0 at baseline to 22.1 at 6-months following treatment)²⁰. As an exploratory calculation, if our assumptions were revised to $\rho = 0.7$, then the corresponding sample size required would be 17 participants.

If we expect up to about 20% attrition in studies such as this, then we will recruit up to a total of 18 participants in this pilot study.

Statistical Plan

Nominal patient characteristics data will be summarized descriptively as number and percent of participants in each category. Ordinal and continuous patient data that are not approximately normally distributed will be summarized as median and interquartile range (IQR). Normally distributed continuous patient data will be presented as mean \pm SD.

STU#:00208657

Version 3.1

11/25/2019

Data required for the primary outcome variable, i.e., mean daily frequency of severe hot flashes in the study sample at 6 months after the intervention vs. the baseline daily frequency of hot flashes in the study sample, will be reported as the mean \pm SD if appropriate, or as the median (IQR) otherwise. The primary outcome data will be evaluated using a paired t-test if the data are approximately normally distributed, or using with the Wilcoxon matched pairs signed rank test if they are not. The mean difference and 95% CI will be calculated. The criterion for rejection of the null hypothesis (i.e. no change over the baseline to 6-month follow-up assessment of the mean weekly frequency of severe hot flashes) will be a two-tailed $p < 0.05$.

For AE analysis, safety and tolerability will be summarized descriptively by providing the frequency of adverse events by severity, type, and attribution.

Differences from baseline and associated 95% CIs will be calculated for planned analyses. Variables that are approximately normally distributed (e.g., hot flash frequency) will be summarized as mean \pm SD. These data at baseline, 1, 3, and 6 months will be compared using the one-way repeated measures analysis of variance with pairwise multiple comparison with baseline made using the Holm-Sidak method when appropriate.

The criterion for rejection of the null hypothesis for all of the secondary analyses will be a two-tailed $P < 0.05$, as this is an exploratory study.

With severe HF frequency selected as the primary outcome, $> 35\%$ reduction from baseline to 6 months will be considered to be clinically significant. However, as this is an exploratory study, a larger reduction was used for the power analysis presented above.

If this study shows meaningful treatment effects in this study population, we plan to further evaluate our hypotheses in a larger, randomized blinded sham controlled study.

We anticipate that results of the current proposed study will provide more accurate estimates of HF frequency and variability than currently available in the literature, and these data can be used to design a rigorous larger RCT.

Given the small sample size, we do not plan on a midterm analysis or futility assessment.

All data will be de-identified and recorded in duplicate on electronic study-specific case report forms (CRFs) REDcap. Participants will be given a study identification number that will be reported on all CRFs and source documents. Only the PI and authorized staff, according to the list of Authorized Study Personnel, are entitled to make entries on the CRF. Personal patient data will be kept confidential. Patient documentation will identify a patient by initials and study number only. The PI will keep in his file a Patient Identification and Enrollment List. To allow compliance with GCP principles, each patient will be asked for consent regarding the access to source documents for monitoring, audits, and inspections. Data both electronic and paper will be destroyed 5 years after manuscript completion using current vendors and department protocol.

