We are currently studying SGB effects in postmenopausal women in a sham-controlled clinical trial funded by the National Institute on Aging (NIA R01AG049924-01; PI [name]).

Given the frequency and severity and interference of HF in men on ADT for prostate cancer, in addition to the negative effects HF impose on this patient population and a paucity of effective treatments, finding alternative treatments for HF in this population is needed.

STU#:00208657

Version 3.1

11/25/2019

3.0 STUDY ENDPOINTS:

Primary Outcome

Change in frequency of weekly hot flashes by self-report hot flash diary between baseline and 3 months following the intervention.

Secondary Outcomes

1. Change in frequency of weekly hot flashes by self-report hot flash diary between baseline and 1 month following the intervention.
2. Change in frequency of weekly hot flashes by self-report hot flash diary between baseline and 6 months following the intervention.
3. the change in hot flash severity (hot flash frequency * hot flash intensity) between baseline and 1, 3, 6 months following the intervention
4. the change in Hot Flash Related Daily Interference Scale (HFRDIS) between baseline and 1, 3, 6 months following the intervention
5. PROMIS SF4a (sleep)
6. Patient Global Impression of Change Score (PGIC)
7. Number and type of adverse events related to SGB according to NCI-CTCAE v5.0.

Mean frequency= $((F_{mi}+F_{mo}+F_{se})/7)$

where F_{mi} , F_{mo} and F_{se} are the weekly total number of mild, moderate or severe/very severe HF events

Mean severity = $(F_{mi}+2\times F_{mo}+3\times F_{se})/7$

where F_{mi} , F_{mo} and F_{se} are the weekly total number of mild, moderate or severe/very severe HF events In the case of mean severity, frequency of mild vasomotor symptoms (VMS) is not counted at baseline

4.0 STUDY INTERVENTION:

Image Guided Right Sided Stellate Ganglion Block with 0.5% Bupivacaine

5.0 PROCEDURES INVOLVED:

5.1 Study design:

We aim to conduct a single-site, open label trial of SGB in men with prostate cancer on ADT.

5.2 Methods & Study Procedures:

Refer to the Section 5.3, Schedule of Events, for additional information.

Visit 1

Consent

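### One sentence in Section 17 defines the primary data with severe hot flashes at 6 months but hot flashes of unstated grade at baseline; both sides should name the same grade and unit.

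*Combined protocol and SAP*

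**What the plan says.** Section 17.0, Statistical Plan, describes the data for the primary outcome as "mean daily frequency of severe hot flashes in the study sample at 6 months after the intervention vs. the baseline daily frequency of hot flashes". The next sentence sends the primary outcome data to a paired t-test or, if they are not approximately normal, to the Wilcoxon signed rank test. The quoted sentence is therefore the working definition of the paired difference.

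The other statements in Section 17.0 read differently:

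- The null hypothesis, in the same paragraph, is "no change over the baseline to 6-month follow-up assessment of the mean weekly frequency of severe hot flashes".
- The Power Analysis gives the primary endpoint as "change in weekly frequency of severe hot flashes at 6 months post-intervention vs. baseline (pre-intervention", and takes the mean severe count from 46.0 to 22.1 per week.
- The clinical threshold of more than 35% is introduced by "With severe HF frequency selected as the primary outcome".

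Section 3.0 gives one formula for mean frequency: mild, moderate and severe/very severe counts are added and divided by 7, where the terms "are the weekly total number of mild, moderate or severe/very severe HF events". This is an all-grade daily figure. Section 3.0 has no formula for a severe-only frequency.

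**The concern.** A paired difference needs the same quantity at both times. Severe flashes are a subset of all flashes. If follow-up counts severe flashes only and baseline counts every grade, the difference contains the baseline mild and moderate flashes whatever the treatment does, and it always points towards benefit.

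Two features of Section 3.0 make it unsafe to rely on the reader to restore the missing word. First, the baseline phrase in the Section 17.0 sentence matches the all-grade daily formula closely. Second, Section 3.0 does treat baseline differently elsewhere: for mean severity, mild symptoms are left out at baseline. A programmer could not assume that symmetry is always intended.

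The primary result would be at stake. The trial is open label with one arm, and its estimates are meant to inform a larger randomised trial.

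**Working it through.** **1. The plan's sample size.** Inputs from Section 17.0, Power Analysis: SD1 = 43, SD2 = 21, ρ = 0.8, Δ = 0.52 × 46.0 = 23.9 per week, two-sided α = 0.05, 80% power.

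SD of the difference = √(SD1² + SD2² − 2ρ·SD1·SD2) = √(1849 + 441 − 1444.8) = √845.2 = 29.07.

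With the noncentral t distribution, the smallest n reaching 80% power is 14 (power 81.1%). At ρ = 0.7 the SD is √(2290 − 1264.2) = 32.03 and n = 17 (power 82.3%). Attrition: 14/(1 − 0.20) = 17.5, so 18. All three stated figures reproduce. They rest on severe flashes at both times, so correcting the sentence leaves them as they are.

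**2. The sentence taken literally.** Let an unchanged man have T flashes per week, of which a share s is severe.

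- Baseline (all grades, per day): T/7
- Follow-up (severe, per day): sT/7
- Apparent reduction: (T/7 − sT/7)/(T/7) = 1 − s

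The documents do not give s. The assumed 46.0 per week is a severe count with no matching total, and the entry threshold of 28 per week is a total with no severe count. The share is therefore an assumption, shown over a range at T = 28 (4.0 per day). At s = 0.8 the apparent reduction is 20%.

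The last column is a simulation of the paired t-test with no true change: n = 14, 4,000 runs, person means of 28 plus an exponential with mean 18 per week, Poisson weekly counts and binomial severe counts. All of these distributions are assumed.

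| Severe share s | Baseline per day, all grades | Follow-up per day, severe | Apparent reduction | Rejection with no true change |
|---|---|---|---|---|
| 0.25 | 4.0 | 1.0 | 75% | 100% |
| 0.50 | 4.0 | 2.0 | 50% | 100% |
| 0.65 | 4.0 | 2.6 | 35% | 100% |
| 0.75 | 4.0 | 3.0 | 25% | 99% |
| 0.90 | 4.0 | 3.6 | 10% | 39% |
| 1.00 | 4.0 | 4.0 | 0% | 5% |

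With severe flashes at both times, the expected difference for an unchanged man is 0, and simulated rejection is 4.6% to 5.4% across the same shares.

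**3. The unit.** Dividing both sides by 7 multiplies the mean difference and its standard error by the same constant. The t statistic, the signed ranks, the p-value and the percentage reduction do not move. Only the printed difference and its confidence interval change scale: the planned 23.9 per week is 23.9/7 = 3.4 per day.

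**The case against.** The strongest reply is that the plan does not prescribe a mixed comparison. The null hypothesis being tested is stated explicitly, two sentences later, and is severe against severe. The power analysis agrees, and so does the sentence on clinical significance. Every other statement of this comparison in Section 17.0 uses severe flashes, so an omitted word is the natural reading. This stands, and it limits the point to a contradiction that needs removing. It does not remove the point, because the sentence at fault is the one that defines the data for the test.

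A reader might also infer that any severe share below 0.65 would meet the 35% criterion with no effect. The arithmetic is right for the mixed difference, but the documents do not apply the criterion to that difference. The "reduction from baseline to 6 months will be considered to be clinically significant" wording follows directly on naming severe flash frequency as the primary outcome, which makes it severe against severe.

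It may further be said that the sentence will be rewritten anyway when Sections 3.0 and 17.0 are reconciled. Section 3.0 gives the primary outcome as "Change in frequency of weekly hot flashes by self-report hot flash diary between baseline and 3 months following the intervention", which differs in both grade and time point. That is the larger conflict. Settling the time point alone would leave this sentence unrepaired; settling the grade would repair it only if the wording is changed at both ends.

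**Conclusion.** The sentence is wrong as written and inconsistent with the rest of Section 17.0. The cause is probably a dropped *severe*.

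If it were followed literally, using Section 3.0's all-grade formula at baseline, a man with some mild or moderate flashes and no change would show an apparent reduction of 1 − s: 20%, 35% or 50% at assumed shares of 0.8, 0.65 or 0.5. These are illustrations under an assumed share, not an estimate of bias in this trial. The simulated rejection rates also depend on assumed count distributions.

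Three stronger conclusions are not supported:

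- That the plan scores every unchanged man as improved. This requires the literal reading, and even then a man whose flashes are all severe shows no change.
- That the daily/weekly switch alters the test. It changes no p-value and no percentage.
- That the sample size is affected. N = 14 stands on the plan's own assumptions.

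**What to change.** Reword the sentence so that grade and unit match at both times. For example: *each participant's weekly number of severe hot flashes at follow-up minus his weekly number of severe hot flashes at baseline*. If all-grade frequency becomes the primary outcome when Sections 3.0 and 17.0 are reconciled, use all grades at both times instead; the power inputs, which describe severe flashes, would then need to be looked at again.

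Add the matching formula to Section 3.0, since none exists there for a severe-only frequency. Report the mean difference and its 95% confidence interval per week, so that they can be set against the planned 23.9.

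The cost is one reworded sentence and one formula line, made before analysis. With severe flashes kept as the primary measure, no new data are needed and the sample size does not change.

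### The primary test is chosen after the outcomes are in, by an undefined normality judgement, and its Wilcoxon branch fits neither the stated mean null nor the reported mean difference

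*Combined protocol and SAP*

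**What the plan says.** All of this is in Section 17.0.

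- **Choice of test (Statistical Plan).** The first branch reads "The primary outcome data will be evaluated using a paired t-test if the data are approximately normally distributed". The fallback, when that condition fails, is worded "or using with the Wilcoxon matched pairs signed rank test if they are not". The text does not say how normality is judged, at what threshold, by whom, or whether on the counts at each visit or on the within-man changes.
- **Null and estimate (Statistical Plan).** The null is no change in mean weekly frequency of severe hot flashes, rejected at a two-tailed 0.05. A mean difference with 95% CI is reported whichever test is used. The type of interval is not named.
- **Sizing (Power Analysis).** The basis is given as "Using a paired one-sample t-test comparing changes between 6-month assessment and baseline". The claim resting on it is that "a sample size of 14 participants will provide 80% power with a two-sided" test at the 0.05 level, for a fall "from a mean of 46.0 at baseline to 22.1 at 6-months following treatment". No power is given for Wilcoxon.
- **Shape.** The Power Analysis says its results "assume the properties of the exponential distribution are approximately valid for the severe hot flashes measure". The Statistical Plan, on the repeated-measures analyses, says "Variables that are approximately normally distributed (e.g., hot flash frequency) will be summarized as mean" and SD.

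Section 5.1 describes a single-site, open-label trial, and the intervention in Section 4.0 is a single block with no comparator. No step is described that fixes the choice of test before the outcomes are examined.

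**The concern.** With about 14 evaluable men, a statement that data are approximately normal is a judgement on which two competent analysts can differ. The plan's two remarks on shape do not tell the analyst which branch to expect. If the result is borderline, the declared outcome of the trial can turn on that judgement.

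There is also a structural mismatch. The signed-rank test is a test of the mean change only if the changes are symmetric. Yet the plan sends the analysis to that test when the data are not normal, which here would usually mean skewed, and it keeps the mean null and the mean difference. A report could then show a significant p-value next to an interval for the mean that covers zero.

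This matters even in a pilot, because the plan keeps a formal rejection rule and says that meaningful effects would lead to a larger randomised, sham-controlled trial.

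**Working it through.** **1. The plan's own figure.** Inputs from the Power Analysis: SD1 = 43, SD2 = 21, rho = 0.8, mean change 23.9, two-sided alpha 0.05.

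SD of change = sqrt(SD1² + SD2² − 2·rho·SD1·SD2) = sqrt(1849 + 441 − 1444.8) = sqrt(845.2) = 29.07.

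Exact paired t power (noncentral t) at n = 14 is 81.1%, and 14 is the smallest n reaching 80%. At rho = 0.7 the SD is sqrt(1849 + 441 − 1264.2) = 32.03 and n = 17. Attrition: 14/0.8 = 17.5, so 18. All three figures reproduce, so the sizing is sound for a paired t-test on the change.

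**2. How the two tests behave at n = 14.** Simulation, 20,000 trials per row. Weekly counts have exponential margins with baseline mean 46. The 6-month mean is 46 (no change), 22.1 (52% fall) or 46 × 0.65 = 29.9 (35% fall, the plan's boundary for clinical significance). The visits are joined by a Gaussian copula with Pearson correlation 0.8. The last row uses normal changes with mean 23.9 and SD 29.07. The switch uses Wilcoxon when Shapiro-Wilk on the changes gives p < 0.05. The copula and the Shapiro-Wilk rule are assumptions, since the plan gives neither.

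Percent of trials:

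| Scenario | t, p<0.05 | Wilcoxon, p<0.05 | Switch | Smaller p | Tests disagree | Wilcoxon only |
|---|---|---|---|---|---|---|
| No change | 4.4 | 5.1 | 5.0 | 5.9 | 2.3 | 1.5 |
| 52% fall | 90.9 | 95.0 | 94.9 | 96.0 | 6.2 | 5.1 |
| 35% fall | 55.4 | 60.1 | 59.9 | 63.9 | 12.2 | 8.5 |
| Normal changes, planned effect | 81.0 | 79.3 | 81.0 | 82.3 | 4.3 | 1.3 |

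A 95% t-interval includes zero exactly when the t-test gives p ≥ 0.05. The last column is therefore the share of trials with a significant Wilcoxon beside a t-interval covering zero: about 5% at a 52% fall and 9% at 35%.

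At correlations of 0.5 and 0.7, disagreement is 11.6% and 9.6% at a 52% fall, and 8.6% and 10.9% at a 35% fall.

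**3. How unsettled the branch is.** With exponential margins and rho 0.8, Shapiro-Wilk rejects normality of the changes in 28% of trials under no change, 46% at a 35% fall and 59% at a 52% fall. The plan's sizing assumption does not predict which branch will be taken.

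**4. The mean null under skewed response.** Assumed model: exponential baseline multiplied by a gamma-distributed individual response (CV 0.6 to 0.8) with zero mean change. Rejection rates are 4.8-6.0% for the t-test, 7.5-9.7% for Wilcoxon and 6.9-8.9% for the switch. In this model the excess over 5% comes mainly from Wilcoxon testing something other than the mean.

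**The case against.** The strongest reply is that both tests are written down in advance and that this is a 14-man exploratory study. An objective switch holds type I error at about 5% in the exponential model, and even reporting the smaller p-value gives only 5.9%. That stands. A reader might infer serious inflation of type I error, and these figures do not support it. Nor do they show the tests disagreeing most of the time: the rate is 6-12% under a real effect and about 2% under none.

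A reader might also infer that the exponential assumption already settles the matter in favour of Wilcoxon. It does not. The Power Analysis glosses the assumption as mean and SD being about equal, and it concerns the measure at a visit. A paired t-test needs near-normal changes, on which the plan says nothing. Skewed counts make skewed changes likely but do not establish them. Wilcoxon also carries a cost for the stated mean null (step 4).

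Doubt over whether raw counts or changes are to be checked is a lesser matter, since a paired test works on changes and the sizing paragraph says so. Nor is there a blind to break in a single-arm trial. What is missing is a rule fixed before the outcomes are examined.

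Finally, the simulation follows Section 17.0 (severe hot flashes, 6 months), whereas Section 3.0 defines the primary outcome as the change in weekly hot flash frequency at 3 months. Section 5.2 requires at least 28 hot flashes a week at entry. If all hot flashes are counted, an exponential baseline with mean 46 puts 1 − exp(−28/46) = 46% of simulated men below that floor. The percentages are therefore illustrative. The mismatch of null, test and interval does not depend on them.

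**Conclusion.** The point holds in a limited form. The primary test is selected on the outcome data by an undefined criterion, the plan's remarks on shape conflict, and the Wilcoxon branch neither tests the stated null nor matches the reported estimate. Nothing elsewhere in the document cures this.

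The main consequence is a borderline conclusion that can depend on an undocumented choice, in roughly 6% of trials at the planned effect and 12% at the plan's own threshold of clinical significance. Error control is a secondary matter: about 5% to 5.9% with exponential margins, and about 7-9% under the switch if individual response is skewed.

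These sizes rest on the assumed copula, the Shapiro-Wilk rule, the assumed response model and a t-interval for the mean difference. The documents do not show that Wilcoxon is the required test. A paired t-test fixed in advance cures the problem equally well and fits the rest of the plan better.

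**What to change.** In the primary-outcome paragraph of Section 17.0, delete the normality condition. Name one primary test on the within-man change, take the 95% CI from that same test, and label the other test a sensitivity analysis.

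- **Paired t-test with its t-interval.** This matches the mean null, the sizing and the reported mean difference, and n stays at 14. Cost: less power than Wilcoxon if changes are skewed, about 91% against 95% at a 52% fall with exponential margins.
- **Wilcoxon signed-rank, if the sponsor prefers it.** Restate the null for that test and report a Hodges-Lehmann estimate with its interval. Cost: about 1.7 points of power if changes are normal (79.3% against 81.0%), and no valid test of the mean if changes are skewed.

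Also reconcile the example that treats hot flash frequency as normal with the exponential assumption in the Power Analysis. The work is a few sentences and needs no new data or visits. It should be done before any outcome data are examined.

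### The repeated-measures contrasts with baseline need their own error terms, because the plan's assumed fall in SD from 43 to 21 breaks the equal-variance condition behind a pooled one

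*Combined protocol and SAP*

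**What the plan says.** The Statistical Plan in Section 17.0 compares approximately normal variables, with hot flash frequency as its example, across the four time points by "one-way repeated measures analysis of variance with pairwise multiple comparison with baseline made using the Holm-Sidak method when appropriate". A separate sentence says: "Differences from baseline and associated 95% CIs will be calculated for planned analyses". The section does not mention sphericity, a Greenhouse-Geisser or similar correction, the error term for the contrasts, or a model with unequal variances.

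The Power Analysis in the same section sets out the variability that the plan expects. "The pre-treatment baseline weekly frequency of severe hot flashes was assumed to be 46.0 ± 43" (mean and SD), and "The results below assumed a value of 21 for SD2", the 6-month SD. It adds: "We allowed the original baseline and 6-month SDs to differ at the two assessment times". It also takes the SD to be roughly equal to the mean, as in an exponential distribution.

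Section 17.0 gives the 6-month comparison its own test: a paired t-test, or the Wilcoxon signed rank test if normality fails, with a mean difference and 95% CI. Section 3.0, however, defines the primary outcome as the change in weekly frequency "between baseline and 3 months following the intervention".

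**The concern.** In a conventional one-way repeated-measures ANOVA, every follow-up contrast uses the same residual mean square, with 3(n-1) degrees of freedom. This is valid only under sphericity, that is, when the differences between every pair of time points have the same variance. A plan that expects the SD to halve after treatment does not expect that. Differences from baseline involve the widely spread baseline values, whereas differences between two follow-ups may be much less variable. Pooling them lends the smaller variance to the contrasts of interest.

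At stake are the confidence intervals and adjusted p-values for change from baseline in the repeated-measures analysis. They could look more precise than 14 men can support. The 3-month contrast deserves most attention, because the ANOVA is the only test that Section 17.0 explicitly specifies for the change that Section 3.0 calls primary.

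**Working it through.** **Inputs from Section 17.0, Power Analysis:** SD1 = 43 (baseline), SD2 = 21 (6 months), correlation ρ = 0.8 (range considered 0.5 to 0.8), difference 23.9, n = 14.

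**Assumed, because the documents do not give them:** the SDs at 1 and 3 months, their correlations with baseline, and the correlations between follow-ups. These are varied below. The plan's SDs are for weekly severe hot flashes. Moving to a daily scale divides everything by 7 and leaves the ratios unchanged.

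**1. The plan's own figures.** Variance of a difference = SD1² + SD2² − 2ρ·SD1·SD2.
- ρ = 0.8: 1849 + 441 − 1444.8 = 845.2, SD 29.07. Exact paired t-test power with n = 14 is 81.1%.
- ρ = 0.7: 1849 + 441 − 1264.2 = 1025.8, SD 32.03. This needs n = 17 (power 82.3%).
- 14/0.8 = 17.5, rounded up to 18 recruited.

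The plan's 14, 17 and 18 all reproduce.

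**2. What pooling does.** With four time points, twice the residual mean square estimates the average of the six pairwise difference variances. The pooled SE of a contrast is √(average/n) on 3(n−1) = 39 df. The contrast's own SE is √(its own variance/n) on n−1 = 13 df.

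**3. Base case: SD 43/21/21/21, all correlations 0.8.**
- Baseline to follow-up: 845.2 (three pairs).
- Follow-up to follow-up: 2 × 441 × (1 − 0.8) = 176.4 (three pairs).
- Average: (3 × 845.2 + 3 × 176.4)/6 = 510.8.
- SE at n = 14: pooled √(510.8/14) = 6.04; own √(845.2/14) = 7.77. The ratio is 0.777, so the pooled SE is 22% too small.
- 95% half-width: about 12.2 pooled against 16.8 own, in flashes per week.

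**4. Coverage of the nominal 95% interval** (simulation, 40,000 trials, n = 14, normal data). Contrasts with their own error term covered about 95% in every row.

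| SDs at 0/1/3/6 months | Correlation with baseline / between follow-ups | SE ratio at 1, 3, 6 months | Pooled coverage at 1, 3, 6 months |
|---|---|---|---|
| 43/21/21/21 | 0.8 / 0.8 | 0.78 (all) | 87% |
| 43/21/21/21 | 0.8 / 0.5 | 0.87 (all) | 91% |
| 43/21/21/21 | 0.8 / 0.9 | 0.74 (all) | 85% |
| 43/21/21/21 | 0.5 / 0.5 | 0.81 (all) | 89% |
| 43/21/21/21 | 0.5 / 0.8 | 0.75 (all) | 85% |
| 43/35/28/21 | 0.8 / 0.8 | 0.93, 0.90, 0.82 | 93%, 92%, 89% |
| 43/43/32/21 | 0.8 / 0.8 | 0.97, 1.02, 0.91 | 94%, 95%, 93% |
| 43/21/21/43 | 0.8 / 0.8 | 0.92, 0.92, 0.98 | 93%, 93%, 94% |
| 43/43/43/43 | 0.8 / 0.8 | 1.00 (all) | 95% |

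**5. Error rates.** With no change in means and equal SDs of 43, the chance of at least one false rejection at the Holm-Sidak first step is 4.6% with the pooled error. If the SD fell to 21 at all follow-ups while the mean stayed put, it would be 10.6% pooled against 3.2% with own error terms. The uncorrected overall F test would then reject 8.3% of the time.

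**6. Skew.** With exponential-type data in the base case, coverage is about 85% pooled and 91% with own error terms.

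**The case against.** The strongest reply is that Section 17.0 never states the error term. Holm-Sidak only adjusts p-values and can be run on separate paired tests, in which case the defect disappears. The sentence on confidence intervals also stands apart from the ANOVA sentence. All of this is true, so the point concerns the conventional form of the named method. It still stands, because nothing in the plan directs the analyst away from that form.

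Four stronger readings are tempting, and the documents do not support them.
- **Every contrast with baseline is too precise.** The SD of 21 is given for 6 months only. If little has changed by 1 month (43/43/32/21), the 3-month contrast has nominal coverage.
- **The family-wise error doubles to about 11%.** That needs the SD to halve with an unchanged mean. Under the plan's premise that SD follows mean, no change in mean implies no change in SD, and the error is near nominal. If the contrasts are run only after a significant F test, which is one reading of the closing qualifier in the ANOVA sentence, the error would be lower still.
- **The 6-month primary comparison is compromised.** It has its own paired test and interval, which do not assume sphericity.
- **These intervals will drive the later trial.** Section 17.0 says that the pilot will supply estimates of hot flash frequency and variability. Pooling the error term changes neither the means nor the SDs at each time point.

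The conflict between a 3-month and a 6-month primary outcome is a separate matter. Resolving it to 3 months might well bring the paired test with it.

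**Conclusion.** The point holds as a correction to the repeated-measures contrasts. Under the plan's own expectation that the SD falls with the mean, the conventional pooled error gives intervals and adjusted p-values that can be too favourable when treatment works.

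The size is a range that rests on assumed 1- and 3-month SDs and correlations. Coverage is about 87% in the base case, and 85% to 91% with SD 21 at every follow-up, baseline correlation 0.5 to 0.8 and follow-up correlation 0.5 to 0.9. It is 89% to 93% if the SD falls gradually, and close to nominal for some contrasts under other patterns. With equal SDs and equal correlations there is no loss.

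The analysis is labelled exploratory, which limits the consequence. It matters more if the 3-month change stays primary and no other test is assigned to it.

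**What to change.** Add to the Statistical Plan in Section 17.0 that each comparison with baseline (1, 3 and 6 months) uses its own paired differences, with their own SD and n−1 df, or the signed-rank test if the differences are clearly non-normal. Apply Holm-Sidak to the three resulting p-values, and compute the 95% CIs from the same paired differences. If the overall F test is kept, state that a Greenhouse-Geisser correction applies.

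The cost is one or two sentences, with no change to data collection or sample size. Under the plan's assumptions the intervals become wider (about ±16.8 instead of ±12.2 flashes per week in the base case). The change does not cure skew: with exponential-type data, paired intervals still cover only about 91%.
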